MEDICAL PROTOCOL (HRP-590)

PROTOCOL TITLE: QuitGuide for American Indians: Aims 2 & 3

VERSION DATE: 11-16-2022

ANCILLARY REVIEWS

DO NOT DELETE. Submit the completed checklist below with your protocol.

Which ancillary reviews do I need and when do I need them?
 
Refer to HRP-309 for more information about these ancillary reviews.
			
Select yes or no	Does your study...	If yes...	Impact on IRB Review
 Yes  No	Include Gillette resources, staff or locations	Gillette Scientific review and Gillette Research Administration approval is required. Contact: [contact]	Required prior to IRB submission
 Yes  No	Involve Epic, or Fairview patients, staff, locations, or resources?	The Fairview ancillary review will be assigned to your study by IRB staff Contact: [contact]	Approval must be received prior to IRB committee/designated review.
 Yes  No	Include evaluation of drugs, devices, biologics, tobacco, or dietary supplements or data subject to FDA inspection?	The regulatory ancillary review will be assigned to your study by IRB staff Contact: [contact] See: https://policy.umn.edu/research/indide	Consider seeking approval prior to IRB submission.
 Yes  No	Require Scientific Review? Not sure? See guidance in the Investigator Manual (HRP-103).	Documentation of scientific merit must be provided. Contact: [contact]	
 Yes  No	Relate to cancer patients, cancer treatments, cancer screening/prevention, or tobacco?	Complete the CPRC application process. Contact: [contact]	
 Yes  No	Include the use of radiation? (x-ray imaging, radiopharmaceuticals, external beam or brachytherapy)	Complete the AURPC Human Use Application and follow instructions on the form for submission to the AURPC committee. Contact: [contact]	Approval from these committees must be received prior to IRB approval;
 Yes  No	Use the Center for Magnetic Resonance Research (CMRR) as a study location?	Complete the CMRR pre-IRB ancillary review Contact: [contact]	These groups each have their own application process.
 Yes  No	Include the use of recombinant or synthetic nucleic acids, toxins, or infectious agents?	Complete the IBC application via eprotocol.umn.edu	

MEDICAL PROTOCOL (HRP-590)

PROTOCOL TITLE: QuitGuide for American Indians: Aims 2 & 3

VERSION DATE: 11-16-2022

 Yes	Include the use of human fetal tissue, human embryos, or embryonic stem cells?	Contact OBAO for submission instructions and guidance	
 Yes	Include PHI or are you requesting a HIPAA waiver?	If yes, HIPCO will conduct a review of this protocol. Contact: [contact]	
 Yes	Use data from CTSI Best Practices Integrated Informatics Core?	The Information Exchange ancillary review will be assigned to your study by IRB staff Contact: [contact]	Approval must be received prior to IRB approval.
 Yes	Formerly the AHC Information Exchange (IE)?		
 Yes	Use the Biorepository and Laboratory Services to collect tissue for research?	The BLS ancillary review will be assigned to your study by IRB staff. Contact: [name] [contact]	These groups do not have a separate application process but additional information from the study team may be required.
 Yes	Have a PI or study team member with a conflict of interest?	The Col ancillary review will be assigned to your study by IRB staff Contact: [contact]	
 Yes	Need to be registered on clinicaltrials.gov?	If you select "No" in ETHOS, the clinicaltrials.gov ancillary review will be assigned to your study by IRB staff Contact: [contact]	
 Yes	Require registration in OnCore?	If you select "No" or "I Don't Know" in ETHOS, the OnCore ancillary review will be assigned to your study by IRB staff Contact: [contact]	Does not affect IRB approval.
 No			

MEDICAL PROTOCOL (HRP-590)

PROTOCOL TITLE: QuitGuide for American Indians: Aims 2 & 3

VERSION DATE: 11-16-2022

PROTOCOL COVER PAGE

1.0 Objectives

1.1 Purpose:

This protocol is for a NIH funded study.

To test feasibility, acceptability, and preliminary efficacy of the tailored QuitGuide for smoking cessation among AIs. Our hypothesis is that the tailored QuitGuide will have higher ratings of feasibility and acceptability compared to the standard, publicly available QuitGuide among AI smokers. Additionally, we hypothesize that the tailored QuitGuide will have similar ratings of feasibility and acceptability among participants in OK compared with participants in MN/WI.

2.0 Background

2.1 Significance of Research Question/Purpose:

There is a need to better serve American Indian (AI) peoples in quitting commercial tobacco use. In many AI tribes, there is a long history of the use of tobacco for ceremonial and spiritual purposes. In the last century, however, the addictive use of commercially produced tobacco has increased dramatically among AI peoples. This disparity is particularly evident in the northern plains region of the U.S. in states such as Minnesota where an estimated 59% of AI adults identified as current smokers relative to 16% of the White population.¹ Consequently, and as shown in prior research by our team, AI peoples experience disproportionately higher rates of tobacco-related morbidity and mortality, such as lung cancer, as much as three-fold more than of White persons.²⁻⁴ While the proportion of AI smokers who attempted to quit in the past year is similar to the general population (53% versus 56%), the percentage of AI ever smokers who are former smokers is roughly half that of the general population (29% versus 56%).^{5,6}

Lower quitting among AI peoples is due to a number of factors, including poor engagement with available treatments. Many factors contribute to low quitting rates among AI peoples, including early age of smoking initiation which is associated with greater dependence,⁷ infiltration of commercial cigarettes into ceremonies, funerals, and pow wows instead of traditional tobacco,⁸ tobacco industry targeting of AIs as shown in our prior research,⁹ stress and historical and contemporary trauma, socioeconomic challenges, and mistrust of health providers. Lack of access to or availability of culturally-tailored treatments is likely another important contributor.

2.2 Preliminary Data:

NCI's QuitGuide is a publicly available smartphone app for cessation. QuitGuide follows US Clinical Practice Guidelines which are the gold-standard in cessation treatment.²⁰ Guidelines call for tracking smoking status, offering quit planning, pharmacotherapy advice, tools to enhance motivation, and social support.²⁰ QuitGuide allows the user to track mood and cravings any time of the day, provides motivational messages and quit tips, and includes GPS technology which allows the user to mark a location as a trigger and then the app sends the user an alert and quit tip if they approach the location. QuitGuide was downloaded >100,000 times from 2015-2018 (personal communication w/[name] at Smokefree.gov; Smokefree.gov is managed by the

MEDICAL PROTOCOL (HRP-590)**PROTOCOL TITLE: QuitGuide for American Indians: Aims 2 & 3****VERSION DATE: 11-16-2022**

National Cancer Institute and the QuitGuide is a Smokefree.gov product). In testing of mainly White smokers without providing pharmacotherapy, QuitGuide was viewed as feasible and potentially efficacious as 8% quit (non-biochemically verified).¹⁵ Although the QuitGuide's quit rate is lower than face-to-face studies that include pharmacotherapy,²¹⁻²³ the reach and therefore the absolute number of people quitting with QuitGuide is potentially far greater. Given prior studies like the aforementioned ANBL that observed numerically lower abstinence among AIs in the non-tailored versus culturally-tailored arm, **we hypothesize that the QuitGuide fails to maximize quitting among AIs, but can be improved if tailored.**

There are several avenues for tailoring the QuitGuide to better fit the culture and needs of AI smokers. QuitGuide uses conventional tobacco control messages that portray tobacco entirely negatively which may be offensive and ineffective among AI persons for whom ceremonial tobacco use is part of spiritual practice. This may be overcome by distinguishing commercial versus traditional tobacco use in the app and embedding previously developed content on traditional tobacco use to reframe how tobacco should be used. Such content may include resources on traditional tobacco use that are publicly available through the National Native Network Keep Tobacco Sacred website.²⁴ Additionally, while the QuitGuide provides guidance to triggers common to the general population such as drinking coffee, it does not include triggers unique to AI persons such as cigarette use at pow wows, funerals, ceremonies and in the home. Since smoking is pervasive in the environments of many AI persons, equipping AIs with how to combat triggers unique to their environment as well as triggers shared with the general population may be particularly effective. Another tailoring avenue is the inclusion of links to short videos on quit tips from AI persons themselves created by CDC's Tips from Former Smokers Campaign.²⁵ An additional avenue for tailoring may include emphasis on younger generations and communities at large to encourage quitting. This could be done through providing the option to upload family photos to the app.

Rigor of prior research and scientific premise of the proposed study:

- There is evidence from our team and others that there is a significant public health problem of commercial smoking among AIs²⁻⁴ and while many AIs want to quit, lifetime quitting is lower among AI peoples compared to those from other racial/ethnic backgrounds.^{5,6}
- While not reaching statistical significance, quit rates in face-to-face interventions such as ANBL were numerically higher if culturally-tailored to AIs.^{10,11} This is also evidence that face-to-face delivery, even if culturally-tailored, suffers from low engagement due to participant barriers like transportation.^{10,11}
- Smartphone-delivered interventions allow for immediate access to interactive, readily tailorabile, treatment content;¹⁵ therefore, these interventions have great potential for reaching and engaging AI smokers.
- QuitGuide is a smartphone app with evidence for cessation efficacy in predominately White smokers.¹⁵ QuitGuide provides real-time guidance on how to navigate triggers resulting from the smoker's environment which could be particularly effective for AIs given the high prevalence of smoking in many AI communities. However, at present QuitGuide does not include guidance on triggers unique to AI persons such as cigarettes use at funerals, pow wows, and by others in the home. Additionally, the QuitGuide uses conventional messages that portray tobacco entirely negatively and does not address traditional tobacco. This is problematic because of our team's data showing that cultural references to traditional

MEDICAL PROTOCOL (HRP-590)

PROTOCOL TITLE: QuitGuide for American Indians: Aims 2 & 3

VERSION DATE: 11-16-2022

tobacco in smoking cessation messages can positively affect message and cessation perceptions (AICAF unpublished data). The need for tailoring the QuitGuide to better fit the needs of AI persons is further supported by prior interventions that showed higher abstinence in groups receiving culturally tailored treatment.^{10,11}

2.3 Existing Literature:

Evidence suggests that culturally-tailored interventions may increase cessation in AIs but face-to-face delivery is costly and hindered by lack of transportation among participants. Prior work by the American Indian Cancer Foundation (AICAF; subcontract on proposal), shows that references to traditional tobacco in cessation messages can positively affect self-efficacy to quit (unpublished data). To our knowledge, only two culturally-tailored cessation interventions for AI peoples exist that purposely engage AI voices throughout the research and utilized rigorous methodology (i.e., included a control group, biochemically confirmed abstinence). The first is the All Nations Breath of Life (ANBL) intervention which was created for AIs representing many tribes and included pharmacotherapy, in-person behavioral support led by AI facilitators, and culturally-tailored curriculum.¹⁰ Biochemically confirmed abstinence was higher in the tailored versus standard group, though the difference between the groups was not statistically significant (11% vs 7%).¹⁰ The second, a tribal-specific program which included pharmacotherapy, also observed higher, but non-significant, abstinence in the tailored versus standard group (23% vs 14%).¹¹ Both studies observed poor retention (~40% loss-to-follow-up) and lack of transportation was a major contributor. Innovative approaches that can reach AI smokers and, that overcome the barrier of travel to an intervention site are needed to address commercial smoking among AI people.

Mobile health (mHealth) interventions, can have broad reach, be delivered conveniently and efficiently, and can be tailored to be engaging and culturally appropriate for AI people, offer promise for overcoming obstacles to delivering the traditional modes of cessation treatment. Web-based and text messaging interventions have the advantage of convenience and may be well-suited for a cessation intervention due to cost effectiveness and scalability. A 2020 U.S. Surgeon General report concluded that these mHEALTH approaches increase cessation.¹² Two ongoing studies are using the web¹³ or text-messaging¹⁴ to deliver culturally-tailored cessation treatment to AIs. **However, the increasing use of smartphones offers a new mHEALTH platform known as smartphones applications (“apps”)** that offer new intervention content modalities and extend elements of the web and texting to create more interactive and visually appealing content. Apps have several features that make them appealing for a smoking cessation intervention: (1) treatment content available at arm's reach, (2) tracking progress anywhere and anytime including tailored support to environments that trigger smoking cues (e.g., car, bar), (3) video/audio capabilities, (4) **after initial download, access without cellular or internet connection** which is particularly advantageous due to our prior research experience with AI persons who can lack minutes or internet connection, and (5) content sharable via social media.¹⁵

High smartphone ownership among AI peoples suggests potential high reach of a smartphone delivered cessation intervention in AI communities. Among U.S. adults in 2019, 81% owned a smartphone.¹⁶ A prior study reported 86% of AI peoples owned a cellular device, but this study did not make the distinction between smartphone versus non-smartphone ownership.¹⁷ However, it is likely that the majority (>60%) of AI peoples own a smartphone based on high ownership estimates regardless of rural (71%) or urban location (81%) and the lowest estimate

MEDICAL PROTOCOL (HRP-590)

PROTOCOL TITLE: QuitGuide for American Indians: Aims 2 & 3

VERSION DATE: 11-16-2022

of ownership was at 66%, which was among persons of low education.¹⁶ Additionally, a 2018 study reported 86% of AI peoples use a smartphone as their news source.¹⁸ **Finally, apps for Indigenous language preservation and revitalization are being used by Tribes, which suggests that apps are a promising platform for delivery of other content to AI peoples.**¹⁹

For all of these reasons, we are now proposing to test the feasibility and acceptability of a culturally-tailored version of the QuitGuide, developed by our team, versus the standard QuitGuide among American Indian persons in MN and WI.

3.0 Study Endpoints/Events/Outcomes

3.1 Primary Endpoint/Event/Outcome:

The primary endpoint, which was used for power and sample size is the frequency of app use during the 5-week period.

3.2 Secondary Endpoint(s)/Event(s)/Outcome(s):

Secondary endpoints:

- Frequency of app use during the 1st week post-randomization
- Frequency of interactions with various app features (e.g. quit tips, trigger list) over the 5 weeks
- Study accrual relative to recruitment goal
- Study attrition measured as percentage of randomized participants that complete the survey at 5 weeks
- Frequency of returning saliva sample by 2 weeks post the week 5 survey (i.e., 7 weeks post randomization)
- Following measures at 5 weeks via exit survey
 - Usability of App Design measured using System Usability scale (SUS)³⁴ Acceptability of overall app (i.e., how likely would you be to recommend the app) and various app components (e.g. quit tips, trigger list) measured as Likert-scale responses

Fit of app with culture measured as Likert-scale responses

Exploratory endpoints:

Following measures at 5 weeks via exit survey

- Number of 24-hour quit attempts over the over the 5 week period
- Self-reported 24-hour abstinence at time of exit survey
- Self-reported 7-day abstinence at time of exit survey
- Self-reported 30-day abstinence at time of exit survey
- Nicotine replacement therapy and pharmacotherapy (e.g. Chantix) use over the 5 week period
- Other behavioral support (e.g. in-person, quitline) for smoking cessation over the 5 week period

MEDICAL PROTOCOL (HRP-590)

PROTOCOL TITLE: QuitGuide for American Indians: Aims 2 & 3

VERSION DATE: 11-16-2022

- Saliva cotinine at 5 weeks for those with 7-day abstinence prior to this time point to biochemically confirm self-reported 7-day abstinence (saliva cotinine < 10 ng/mL)

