4.0 Study Intervention(s)/Investigational Agent(s)

4.1 Description:

Participants will be randomized to either the tailored QuitGuide app or the standard version of the QuitGuide app for 5 weeks. Specifically, participants will be asked to use the assigned app for one week pre-quit and 4 weeks.

Tailored QuitGuide app

This is an app not available to the public. It was developed/tailored based on an app titled QuitGuide that is available to the public and can be downloaded. Screen shots of the publicly available version, referred to as the Standard QuitGuide app, are provided as an attachment. We have also included a document describing the changes and updates that were made to the Standard QuitGuide app to develop the Tailored QuitGuide app.

Standard QuitGuide app

This is an app titled QuitGuide that is available to the public and can be downloaded and screen shots are provided as an attachment. We will not provide all photos but several options are included in the IRB submission.

4.2 Drug/Device Handling:

This study does not use a drug. The study will not be providing any device to participants. They will be expected to use their own cell phone for accessing the QuitGuide app.

4.3 Biosafety:

No biosafety concerns or reviews required.

4.4 Stem Cells:

This study does not use stem cells.

4.5 Fetal Tissue:

This study does not use fetal tissue.

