5.0 Procedures Involved

5.1 Study Design:

This is a two-arm randomized clinical trial of the tailored vs standard QuitGuide app conducted.

5.2 Study Procedures:

To test feasibility, acceptability, and preliminary efficacy of the tailored QuitGuide versus standard QuitGuide for smoking cessation among AI peoples.

1. **Telephone Screener:** We will recruit AI smokers interested in quitting. Individuals will be screened over the phone for eligibility.

MEDICAL PROTOCOL (HRP-590)

PROTOCOL TITLE: QuitGuide for American Indians: Aims 2 & 3

VERSION DATE: 11-16-2022

2. **Phone-Based Baseline Interview:** If eligible, then consent will be completed. Then, participants will complete a REDCap survey (titled Baseline Survey—see below for measures). Participants will be randomized to either the *Tailored QuitGuide app* or the *Standard QuitGuide app*. Participants will be provided instruction on how to download the app to their smartphone. Upon download, all participants will be asked to provide a unique participant app ID in the app.

Randomization: Participants will be randomized with equal probability to either a tailored version of the NCI QuitGuide or a standard version of the NCI QuitGuide. Randomization will be stratified by rural/urban clinic, male/female gender, and <50 years of age/50+ years of age. Randomization will be completed using permuted block randomization with random block sizes of 2 and 4. We anticipate no or minimal block effects in our data, and therefore, we will not account for block effects in our data analysis. The randomization schedules will be created in advance.

3. **App interaction:** Upon opening the app for the first time, participants will be asked to set a quit date. All participants will set their quit date for one week later to standardize pre- and post- quit times. If smoking relapse occurs, participants will be provided the option to reset the quit date as this flexibility is permitted in the QuitGuide. Each participant will be asked to use the app for 5 weeks. Participants will have the option to contact the research coordinator at any time to report issues. At week 4, participants will be mailed a letter reminding them of the exit survey and will provide routine saliva sample collection kit with instructions to provide the sample on the same day of their exit survey, and materials (e.g., pre-paid envelope) to return the sample to the University of Minnesota for analysis.

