4. **Exit Survey:** At the end of the day on the last day of the 5 weeks of app use (i.e., 5 weeks + 1 day), an automated survey link from REDCap will be sent to participants email to assess self-report outcome measures. Participants will also be called and texted to remind them to complete the survey.
5. **Optional end of study interview:** Those randomized to the tailored QuitGuide may be asked to participate in a follow-up interview to get their feedback on using the app. We expect asking up to 10 people to complete this interview.

All measures are displayed in the table:

Baseline survey collected via REDCap: Demographics, America Indian Identity Measures, Internet and smartphone use, Traditional Tobacco Use, Commercial Tobacco History, Nicotine Dependence Scale, Contemplation Ladder, Environmental Smoke Exposures, Health Literacy, Alcohol consumption, Financial Strain, Perceived Stress Scale, Brief Resilience Scale, Everyday Discrimination Scale
--

Data collected through using app and transferred from SmokeFree.gov:

All app user data. Any and all interactions with the app including days and frequency of use each day and which app components are accessed.
--

MEDICAL PROTOCOL (HRP-590)

PROTOCOL TITLE: QuitGuide for American Indians: Aims 2 & 3

VERSION DATE: 11-16-2022

Exit survey collected via REDCap: Contemplation Ladder TimeLine follow-back calendar to assess self-report CPD, use of any pharmacotherapy, 24-hour quit attempts, use of other cessation resources, Minnesota Nicotine Withdrawal Scale, Usability of App Design by System Usability Scale (SUS) Acceptability measures; plus open-ended responses on app
Audio recordings from the interviews among a subset of the participants
Saliva Sample

5.3 Study Duration:

- Individual participant duration is 5 weeks.
- The duration to enroll all study participants is 1.5 years.
- The duration for all data collection and analysis is 2.5 years.

5.4 Use of radiation:

The study does not use any radiation.

5.5 Use of Center for Magnetic Resonance Research:

The study does not use any CMMR resources.

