8.0 Study Population

8.1 Inclusion Criteria:

- American Indian person based on self-report
- Age \geq 18 years
- Interested in quitting smoking
- Smoke \geq 3 commercial tobacco cigarette per day (CPD) in the past 30 days
 - Use of other commercial tobacco products (e.g., e-cigarettes) is permitted if they report cigarettes being their primary product
- Smartphone ownership with the ability to download applications and sufficient data to complete research procedures

8.2 Exclusion Criteria:

- New or change in pharmacotherapy for smoking cessation (includes: nicotine gum, patch, lozenge, inhaler OR medications Chantix/Wellbutrin/Zyban/Bupropion) in past month

MEDICAL PROTOCOL (HRP-590)

PROTOCOL TITLE: QuitGuide for American Indians: Aims 2 & 3

VERSION DATE: 11-16-2022

- Does not speak or read English

8.3 Screening:

Individuals are screened for eligibility by undergoing a phone screening interview with a research coordinator. The screening consists of questions about eligibility criteria. Participants who are eligible can then complete informed consent and enroll into the study—see informed consent section.

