11.0 Local Recruitment Methods

11.1 Recruitment Process:

Recruitment will occur through social media and community events and news outlets. We also have recruited participants in one prior study (IRB: STUDY00012471: QuitGuide for American Indians: Aim 1 In STUDY00012471, we included a telephone screener form that specifically asks participants "Would you be interested in being contacted by us in the future if other research opportunities become available?". Those participants who responded "Yes" will be re-contacted by IRB approved study personnel on IRB: STUDY00012471 and reminded that they are being re-contacted due to their interest in future studies that was reported when they participated in IRB: STUDY00012471.

11.2 Identification of Potential Participants:

All participants will self-identify based on posted flyers and other recruitment materials OR recruited from IRB: STUDY00012471.

11.3 Recruitment Materials:

Pre-approved scripts and images will be used to develop flyers and postings.

11.4 Payment:

A ClinCard (Greenphire through UMN) gift card will be provided as a physical card mailed to the participant. Payment will be made as participant completes the following tasks:

Total possible compensation for all participants is \$125. Those asked to participate in a follow-up survey can receive an additional \$25.

1. Telephone Screener: No payment
2. Virtual Baseline Interview: \$25 payment
3. App interaction: No payment
4. Exit survey: \$25 if completed within 48 hours or else \$10 if completed not within 48 hours
5. Returned saliva sample: \$25 payment
6. Bonus for completing all study procedures: \$50
7. Follow-up interview among a subset of participants, invite only: \$25 additional.

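### The exploratory 30-day abstinence look-back is slightly longer than the roughly 28 to 29 days planned between the set quit date and the exit-survey link.

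*Combined protocol and SAP*

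**What the plan says.** - **Endpoint.** Section 3.2 lists "Self-reported 30-day abstinence at time of exit survey" beside 24-hour and 7-day abstinence, all collected by the exit survey. Section 15.1 analyses each as a binary outcome, adjusted for the stratification factors.
- **Quit date.** Section 5.2 anchors it to the app: "Upon opening the app for the first time, participants will be asked to set a quit date". It then fixes the interval: "All participants will set their quit date for one week later to standardize pre- and post- quit times". A reset is allowed after relapse.
- **Planned periods.** Section 4.1: "participants will be asked to use the assigned app for one week pre-quit and 4 weeks".
- **Survey.** Section 5.2 sends the link "At the end of the day on the last day of the 5 weeks of app use (i.e., 5 weeks + 1 day"). It adds: "Participants will also be called and texted to remind them to complete the survey". Section 11.4 pays $25 for a reply within 48 hours and still pays $10 "if completed not within 48 hours". No closing date is stated.
- **Entry status.** Section 8.1 requires at least 3 "commercial tobacco cigarette per day (CPD) in the past 30 days".

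Sections 3.2, 5.2 and 15.1 neither tie the 30-day window to the quit date nor give a grace rule. The wording of the survey item is not reproduced in the documents.

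**The concern.** The protocol standardizes the time before and after quitting, and then chooses a longest abstinence window that does not fit inside the time after. On the day the link arrives, a 30-day look-back generally takes in a day or two when the plan still expects the participant to be smoking. Someone who follows the schedule exactly and answers promptly is then scored a failure on this item.

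Because the score is yes or no, a gap of one or two days is enough to change it. Replies will not all come on the same day: the link is emailed, reminders follow, and late replies are accepted. The section 15.1 model has no term for days from quit date to reply. Preliminary efficacy is one of the stated purposes (section 1.1), and this is the longest abstinence measure offered for it. At stake is how that one rate can be read.

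**Working it through.** The plan gives no figure for the 30-day measure. Its sample-size calculation (section 15.2) concerns app use and has no bearing here. The one total to reproduce is the schedule: 7 days pre-quit + 28 days after = 35 days = 5 weeks, which agrees with section 4.1.

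**Step 1: elapsed time at the link.** Take opening as day 0. The quit date is day 7, and the link goes out on day 35 or, with the extra day, day 36.

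- Elapsed since quit date = link day − quit day: 35 − 7 = 28, or 36 − 7 = 29.
- Shortfall = 30 − elapsed: 2 days or 1 day.

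The shortfall is also the reply delay needed before someone who stopped on the set date can truthfully answer yes.

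**Step 2: sensitivity to day counting.** Now number the day of opening as day 1, so the quit date is day 8. The link day N can be read as 35 (last day of the 5 weeks), 36 (one day later) or 37 (5 weeks and 1 day after opening).

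| Link day N | Quit day not counted: N − 8 | Shortfall | Quit day counted: N − 7 | Shortfall |
|---|---|---|---|---|
| 35 | 27 | 3 | 28 | 2 |
| 36 | 28 | 2 | 29 | 1 |
| 37 | 29 | 1 | 30 | 0 |

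The elapsed time is 27 to 30 days and the shortfall 0 to 3 days. One convention gives no shortfall. The cells are alternative readings of the same text, not equally likely outcomes, so counting them says nothing about probability.

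**Step 3: who can score yes on the link day.** The latest qualifying stop day is N − 30 = 5, 6 or 7 (stop day not counted), or N − 29 = 6, 7 or 8 (counted). That is 3 to 0 days before the set quit date on day 8. Stopping slightly early is enough.

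**Step 4: start of the survey clock.** The above assumes that the 5 weeks run from first opening, or that the app is opened on the day of randomization. Section 3.2 equates two weeks after the week 5 survey with 7 weeks after randomization, which points to a randomization clock; section 5.2 counts weeks of app use. If the clock runs from randomization and opening is k days later (k is my assumption), the elapsed time becomes 28 − k to 29 − k days:

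- k = 1: 27 to 28 days, reply delay needed 2 to 3 days
- k = 3: 25 to 26 days, delay 4 to 5 days
- k = 7: 21 to 22 days, delay 8 to 9 days

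This would widen the mismatch, but the point does not depend on it.

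**The case against.** The strongest reply is that nothing is misclassified. The endpoint looks back from the survey, not from the quit date. A person abstinent for 28 days who answers no is correctly scored, and so is the same person answering yes two days later. That stands. A reader might infer that 30-day abstinence is unattainable on this schedule; step 3 shows that it is not.

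Second, dependence on reply day is common to every look-back item. Someone who stopped six days before the link changes score on the 7-day item by waiting a day. That also stands. What is particular to the 30-day item is that its window exceeds the planned post-quit period, so even a participant who keeps to the schedule is caught. The 24-hour and 7-day windows fit well inside that period.

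Third, a reader might infer that assessment time is uncontrolled. It is not: the day the link is sent is fixed, reminders follow, and prompt replies earn more. Only a closing date is missing.

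Fourth, the data for a better measure may already be collected. Section 5.2 lists the follow-back calendar together with quit attempts, pharmacotherapy and other cessation resources, and section 3.2 defines those over the 5 weeks. This suggests, without proving, that the calendar covers the whole period. It weakens the concern and makes the repair easier.

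Finally, few people could be affected. If the 8% self-reported quit rate cited in section 2.2 applied here (an assumption), 0.08 × 116 ≈ 9 participants would quit, and only those who stopped close to the set date could change score. The 30-day comparison would be imprecise with either window.

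**Conclusion.** The mismatch holds as a minor point, with moderate confidence. The 30-day look-back is usually 1 to 2 days longer than the time from the set quit date to the survey link (0 to 3 days across conventions). It tends to give a lower rate than a window matched to the 4 post-quit weeks, and a noisier one, because some scores turn on a day or two of reply time. How many participants this touches cannot be computed from the documents.

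A reader might go further and infer a biased comparison between arms. The documents do not support that: both arms share the schedule, and nothing shows that reply timing or delay in opening the app would differ by arm. The primary endpoint, app use, is unaffected.

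The conclusion assumes that the survey item carries no rule of its own. Its wording is not in the documents, so this cannot be checked, and it is one reason for moderate confidence. The day-counting convention that leaves no gap is another.

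**What to change.** 1. In sections 3.2 and 15.1, define the longest abstinence measure as a 28-day (4-week) window on fixed study days, from the set quit date to the end of week 5. With opening as day 1 this is days 8 to 35, and 35 − 8 + 1 = 28. The score then no longer moves with the reply day.
2. Derive it from the timeline follow-back calendar already in the exit survey, and state the calendar's look-back. A reply on day R needs R − 8 days to reach the quit date, so a 30-day look-back serves replies up to day 38 and a 35-day look-back serves replies up to day 43.
3. In section 5.2, state whether the 5 weeks to the survey run from first opening or from randomization, and give a closing date for the survey.
4. If the 30-day item is kept for comparability, report it descriptively, with the days from quit date to survey completion.

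The cost is one endpoint definition, two clarifications and a check of the calendar. No new data are needed if its look-back is long enough. The downside is slightly less direct comparability with studies that report 30-day abstinence.
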